#### Experimental design

The objective is descriptive with no performance requirements and no pass or fail criteria. All Phase 2 subjects will be included in this analysis.

#### Presentation format

Results will be described in summary statistics with median and standard deviation. Depending on the amount of data gathered during the clinical study a student t-test can be performed.

Philips IGT Systems Status: Final	Post-Market Clinical Study Plan Contrast volume reduction during PCI with the use of Dynamic Coronary Roadmap	XCY607-130198 2017 Aug 15 Revision: 1.0 Page 13 of 16
---	---	--

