#### Presentation format

Results will be described in summary statistics with median, confidence interval and standard deviation. Depending on the amount of data gathered during the clinical study a student t-test can be performed.

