#### Endpoint

The endpoint is the demographical information of the study population. This will be defined as medical status and history, age, BMI and gender.

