#### Presentation format

Results will be described in summary statistics with median and standard deviation. Depending on the amount of data gathered during the clinical study a student t-test can be performed.

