### 5.2.4. Secondary objective: Procedural information

#### Objective

Collecting procedural information to further define the study population

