#### Endpoint

The endpoint is procedural information. This is defined as information on treated vessels, number of lesions, number of stents, type of lesion, catheter access site, lesion complexity, IVUS usage, OCT usage and FFR usage. These endpoints are typically recorded for patients undergoing coronary interventions, also for non-study patients.

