## 6. DATA MANAGEMENT

Electronic Case Report Form (e-CRF) will be used to collect medical history, subjects demographics, procedure related information, protocol deviations, adverse events and device deficiencies. The e-CRF will be used for data review, data cleaning and issuing and resolving queries. This e-CRF is a web-based e-CRF which is password protected and is 21 CFR part 11 compliant. At the end of the study the data will be stored as a frozen dataset and will be retained.

Raw image data is collected directly from the detector, and therefore is free from any subject information. All other exported data will be de-identified. This data will be collected and stored in a secure location.

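### Sections 5.2.2 and 5.2.4 name only median and SD, with an optional t-test, for item lists that are mostly categorical; counts and percentages should be stated (minor)

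*Protocol*

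**What the plan says.** Section 5.2.2 lists the demographic items: "This will be defined as medical status and history, age, BMI and gender". Section 5.2.4 lists nine procedural items, beginning: "This is defined as information on treated vessels, number of lesions, number of stents, type of lesion, catheter access site, lesion complexity, IVUS usage"; use of OCT and of FFR completes the list.

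Both sections give the same presentation format: "Results will be described in summary statistics with median and standard deviation". Both add: "Depending on the amount of data gathered during the clinical study a student t-test can be performed". Counts, percentages or any other categorical summary are not mentioned in these sections or elsewhere in Section 5.

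For contrast volume, radiation and procedure time (5.1, 5.2.1, 5.2.3), which are all numeric, the format is: "Results will be described in summary statistics with median, confidence interval and standard deviation".

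The aim in 5.2.4 is: "Collecting procedural information to further define the study population". Section 5.2.2 has the parallel aim for demographics. The protocol Summary adds that the secondary information will feed into the design of a later pivotal trial. Both sections also state: "The objective is descriptive with no performance requirements and no pass or fail criteria".

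**The concern.** A median and an SD describe a numeric variable. Most of the items in these two sections are attributes: sex, lesion type, access site, whether an imaging or pressure device was used. To give such an item a median or an SD, someone must first attach numbers to its categories. Where there are three or more unordered categories those numbers are arbitrary, and so is the result.

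What is at stake is the description of the population. These two objectives exist to say who was treated and how. The description also helps a reader judge whether the Phase 2 patients resemble the 25 retrospective patients with whom they are compared without randomization. For that, the reader needs to know how many patients fell in each category.

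The protocol is not silent here. It names a method, and the method does not suit most of the items to which it is assigned.

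**Working it through.** The protocol gives no figure on this point, so there is none to reproduce. The check has four steps.

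**1. Classify the items.** 4 demographic + 9 procedural = 13.
- Numeric (4): age, BMI, lesion count, stent count.
- Categorical on ordinary reading (7): medical status/history, gender, lesion type, access site, and use of IVUS, OCT and FFR.
- Dependent on recording that is not described (2): treated vessels, lesion complexity.

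The categorical share is therefore 7 to 9 of 13. Medical status/history is also undefined. If it is counted as two items, the share becomes 8 to 10 of 14; if it proved numeric, the lower end would be 7 − 1 = 6 of 13.

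**2. Nominal item with three levels.** n = 25 is the Phase 2 size in Section 4.4. The category counts are assumed. Number the categories 1, 2, 3, and let a and c be the counts in the categories numbered 1 and 3. Then

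SD² = [(a + c) − (c − a)²/25] / 24.

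For counts 15, 4 and 6:
- category with 4 patients numbered 2: [21 − 81/25]/24 = 17.76/24 = 0.740, SD 0.86
- category with 6 patients numbered 2: [19 − 121/25]/24 = 14.16/24 = 0.590, SD 0.77
- category with 15 patients numbered 2: [10 − 4/25]/24 = 9.84/24 = 0.410, SD 0.64

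The patients are the same in all three cases. Across all 276 ways of dividing 25 patients over three occupied categories, the SD changes with the numbering in every one.

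The median is the 13th ordered value. If no category holds more than 12 patients (78 of the 276 divisions), it is always 2, so it points to whichever category was given that number. With 12, 3 and 10 patients numbered in that order, the median category is the one with 3 of 25 patients (12%).

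**3. Optional t-test on such an item.** Counts chosen to illustrate: 12, 3, 10 in one group and 8, 11, 6 in the other.
- Numbered in that order, both means are 48/25 = 1.92, so the t-test gives p = 1.00. The reversed numbering gives the same.
- The other four numberings give p = 0.028 to 0.038.
- The chi-square test does not depend on numbering. Expected counts are 10, 7 and 8 in each group, so the statistic is 2 × (4/10 + 16/7 + 4/8) = 6.37 on 2 df, p = 0.041.

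**4. Yes/no item.** With k of 25 positive, SD = √[k(25 − k)/600]. For k = 5 this is 0.408 and for k = 12 it is 0.510, whether the coding is 0/1, 1/2 or reversed. The median shows only which answer is in the majority: 20% and 48% both give 0 under 0/1 coding. Together, exact median and SD identify all 26 possible counts. At two decimals only 11 v 12 and 13 v 14 merge, a difference of 1/25 = 4 percentage points. The percentage is hidden from the reader but is almost fully recoverable.

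**The case against.** The strongest reply is that table layout is usually left to an analysis plan or table shells. Only the protocol is at hand, and a general sentence about summary statistics need not exclude frequencies. Nothing says that lesion types will be given numbers. The sentence may simply be a standard one that applies where it can, and a competent analyst would probably report percentages anyway. The introduction to Section 5 also allows departures from plan if they are justified in the end report.

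This supports a low rating but does not remove the point. The protocol names a statistic for these lists, and the introduction to Section 5 treats what follows as the planned analysis. Read literally, a frequency table in place of the named summary would be a deviation needing justification.

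Three further limits stand. Section 5.2.4 gives no levels for lesion type, treated vessels or access site, and any of them could be two-level or ordered, so the number exposed to the numbering problem may be zero. If lesion complexity is ordinal or a score, its median is meaningful. The enumeration counts possible tables and is not the probability that anything goes wrong in this study.

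A reader might infer more in three directions:
- That 7 to 9 items would be reported meaninglessly. The documents do not support this: gender and the three device-use items lose readability only, and the content of medical status/history is not described.
- That the sentence was deliberately tailored to these endpoints, because it omits the confidence interval found in 5.1. The wording does differ, but the reason is not stated.
- That median with SD is wrong for age, BMI and the two counts. The pairing is unusual, but no error follows from it.

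**Conclusion.** The point holds as a minor fault in a stated method. Median and SD are the only summary, and the t-test the only test, named for 13 items of which about 7 to 9 are categorical. For 0 to 3 of them (lesion type, treated vessels, access site, if nominal with three or more levels) the named statistics depend on arbitrary numbering and do not show the distribution. For the four yes/no items the percentage is obscured.

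The consequence is confined to two descriptive secondary objectives with no success threshold. The primary endpoint and the sample size are not affected. The underlying data are captured in any case: "Electronic Case Report Form (e-CRF) will be used to collect medical history, subjects demographics, procedure related information". It is still worth correcting, because describing the population is the whole purpose of these two objectives.

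The conclusion rests on an ordinary reading of the item names. The numerical examples rest on assumed counts with n = 25.

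**What to change.** In the presentation format of 5.2.2 and 5.2.4, state that categorical items are presented as counts and percentages. Keep numeric summaries for age, BMI and the lesion and stent counts. The loosely described items (medical status/history, treated vessels, lesion complexity) then follow whichever rule matches how the e-CRF records them. If a categorical item is compared with the retrospective group, name Fisher's exact or the chi-square test in place of the t-test.

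The cost is one or two sentences in each section. No new data are needed.

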## 6. DATA MANAGEMENT

Electronic Case Report Form (e-CRF) will be used to collect medical history, subjects demographics, procedure related information, protocol deviations, adverse events and device deficiencies. The e-CRF will be used for data review, data cleaning and issuing and resolving queries. This e-CRF is a web-based e-CRF which is password protected and is 21 CFR part 11 compliant. At the end of the study the data will be stored as a frozen dataset and will be retained.

Raw image data is collected directly from the detector, and therefore is free from any subject information. All other exported data will be de-identified. This data will be collected and stored in a secure location.

### 6.1. Retention period

The investigator shall maintain the records related to this study during the research and for a period according to the national regulation.

Philips will maintain the records for a period of device End of Life (EoL) plus 15 years.

The sponsor and principal investigator shall take measures to prevent accidental or premature destruction of these documents.

## 7. AMENDMENTS TO THE CLINICAL STUDY PLAN

Non-significant changes of the Clinical Study Plan may be included (minor logistical or administrative changes not effecting the rights, safety and well-being of human subjects or not related to the clinical research objectives or endpoints), without prior approval. A simple notification to the IRB and where appropriate regulatory authorities will be made by the Sponsor. Significant changes (such as device modifications, study procedures) shall be discussed with the principal investigator prior approval. All changes will be documented with a justification and described in the latest version of the Clinical Study Plan.

## 8. DEVIATIONS FROM THE CLINICAL STUDY PLAN

The Investigator is not allowed to deviate from the Clinical Study Plan or to enroll subjects that do not comply with all inclusion and exclusion criteria. Under emergency circumstances, deviations from the Clinical Study Plan to protect the rights, safety and well-being of human subjects may proceed without prior approval of the sponsor and the IRB. Such deviations shall be documented and reported to the sponsor and the IRB as soon as possible

All deviations from the Clinical Study Plan will be documented with date, subject, reason, actions taken and if the deviation affects subject's rights, safety and wellbeing or the scientific integrity of the clinical research. The deviation shall be notified to the Sponsor via the e-CRF as soon as possible. Deviations will be reviewed by the sponsor. In case of serious or repetitive deviations, a corrective action plan may be necessary. In some cases suspension of enrollment at the site or disqualification of the site is necessary.

## 9. DEVICE ACCOUNTABILITY

Access to the study device shall be controlled and the study devices shall be used only in the clinical research and according to the Clinical Study Plan.

The sponsor shall keep records to document the physical location of all study devices from shipment of study device to the research sites until return or disposal.

The principal investigator shall keep records documenting the receipt, installation, use, return and disposal of the study device, including date of receipt, identification of each study device and date on which the study device was returned.

## 10. STATEMENTS OF COMPLIANCE

This clinical study shall be conducted in accordance with the clinical study plan, and with the ethical principles that have their origin in the Declaration of Helsinki and all applicable regional and/or national regulations. Furthermore, in Europe this clinical study shall be conducted as much as possible with the International Standards ISO 14155 Clinical investigation of medical devices for human subjects - Good

Philips IGT Systems  Status: Final	Post-Market Clinical Study Plan  Contrast volume reduction during PCI with the use of Dynamic Coronary Roadmap	XCY607-130198 2017 Aug 15 Revision: 1.0 Page 14 of 16
---	---	--

clinical practice and the Medical Device Directive (MDD). Investigators located in the US shall follow: 21 CFR part 50, 56 and 812.

This study shall not be started prior to obtaining a favorable opinion from a Medical Ethics Committee (MEC)/Institutional Review Board (IRB), if required. Any additional requirements imposed by the MEC/IRB shall be followed.

Insurance shall be provided for the subjects participating in this clinical trial according to local law.

## 11. INFORMED CONSENT PROCESS

Informed consent will be obtained from every subject in writing by the Investigator or his authorized designee before the clinical study is started. The subject will be informed both orally and in writing about all aspects that are relevant to the subject's decision to participate in the clinical study, including the clinical study procedures. Ample time should be provided for the subject to read and understand the informed consent form and to consider participation. The informed consent will include personally dated signatures of the subject and the principal investigator or an authorized designee responsible for conducting the informed consent process. A copy of the signed and dated informed consent form and any other written information will be provided to the subject.

Subjects who are unable or unwilling to provide informed consent will not be included in the Research.

If new information becomes available that might significantly affect the subject's future health and medical care, it shall be provided to the subjects in written form. If relevant, subject shall be asked to reconfirm their continuing informed consent in writing.

### 11.1. Subject unable to read or write

Informed consent shall be obtained through a supervised oral process if a subject or legally authorized representative is unable to read or write. An independent witness shall be present throughout the process. The written informed consent form and any other information shall be read aloud and explained to the prospective subject or his/her legally authorized representative and, whenever possible, either shall sign and personally date the informed consent form. The witness also signs and personally dates the informed consent form attesting that the information was accurately explained and that informed consent was freely given.

## 12. SAFETY REPORTING

The following event should be reported to Philips for Medical Device Reporting (MDR) according to 21 CFR part 803: Deaths and serious injuries that a device has or may have caused or contributed to, caused or contributed means that a death or serious injury was or may have been attributed to a medical device, or that a medical device was or may have been a factor in a death or serious injury, including events occurring as a result of: (1) Failure; (2) Malfunction; (3) Improper or inadequate design; (4) Manufacture; (5) Labeling; or (6) User error.

Medical Device Reporting shall be reported to the regular Philips Healthcare customer feedback system, i.e. contact the local Helpdesk to report these events. Also report these to the Clinical Scientist (see Appendix II: List of monitor(s)/Clinical Scientist(s)).

## 13. EARLY TERMINATION OR SUSPENSION OF THE CLINICAL STUDY

There are no provisions or interim analyses planned that can result in an early termination of the trial. Serious or repetitive occurrence of deviations from study protocol or non-compliance with regulations may also be reason for early termination or suspension of a study site.

## 14. PUBLICATION POLICY

It is the intention of the investigator and sponsor to submit the clinical study data for publication. Prior to submission, claims on intellectual property will be assessed.

This study will also be registered on [clinicaltrial.gov](http://clinicaltrial.gov) before first enrollment.

Philips IGT Systems Status: Final	Post-Market Clinical Study Plan Contrast volume reduction during PCI with the use of Dynamic Coronary Roadmap	XCY607-130198 2017 Aug 15 Revision: 1.0 Page 15 of 16
---	---	--

## 15. ABBREVIATIONS USED

Abbreviations	Explanation of abbreviation
CAD	Coronary Artery Disease
CFR	Code of Federal Regulation
CHF	Congestive Heart Failure
CI-AKI	Contrast Induced Acute Kidney Injury
CIN	Contrast Induced Nephropathy
CM	Contrast Medium
CRF	Case Report Form
DM	Diabetes Mellitus
e-CRF	Electronic Case Report Form
e-GFR	Estimated Global Filtration Rate
FDA	Food Drug Administration
FFR	Fractional Flow Reserve
iABP	Intra-Aortic Balloon Pump
IFU	Instructions for Use
IRB	Institutional Review Board
IVUS	Intravascular Ultrasound
OCT	Optical Coherence Tomography
PCI	Percutaneous Coronary Intervention

